1. STUDY ADMINISTRATIVE STRUCTURE

No committees have been formed. All critical decisions were taken in plenum by the involved personnel.

1.4 Laboratory

No laboratory is involved in the study.

1.6 Data Safety Monitoring Committee

In this study of risk category A no specific DSMC is needed. All the interventions performed and the Product tested are associated with extremely low risk factors and therefore possible safety issues can and will be reported and handled in plenum by the principal investigators and responsible personnel.

1.7 Any other relevant Committee, Person, Organisation, Institution

Not applicable.

2. ETHICAL AND REGULATORY ASPECTS

2.1 Study registration

The study is intended to be registered on the SNCTP (automatically through this application) and before initiation of the project also in a WHO primary register (ClinicalTrials.gov).

2.2 Categorisation of study

Clinical investigations or other studies of medical devices, risk category A.

2.3 Competent Ethics Committee (CEC)

The responsible investigator at Rehaklinik Bellikon ensures that approval from the Ethikkommission Nordwest- und Zentralschweiz (EKNZ) is sought for the clinical study.

The responsible investigator as well as all the involved personnel in the study has the duty to report all changes in research activity, unanticipated problems involving risks to humans and premature study end to the CEC. Further, no changes can be made to the protocol without prior Sponsor and CEC approval, except where necessary to eliminate apparent immediate hazards to study participants.

Premature study end or interruption of the study is reported within 15 days. The regular end of the study is reported to the CEC within 90 days, the final study report shall be submitted within one year after study end. Amendments are reported according to chapter 2.10.

2.4 Competent Authorities (CA)

As the only CA in this study is the CEC (risk category A), the section 2.3 applies.

2.5 Ethical Conduct of the Study

The study will be carried out in accordance to the protocol and with principles enunciated in the current version of the Declaration of Helsinki, the guidelines of Good Clinical Practice (GCP) issued by ICH, the European Directive on medical devices 93/42/EEC and the ISO Norm 14155 and ISO 14971, the Swiss Law and Swiss regulatory authority's requirements. The CEC and regulatory authorities will receive annual safety and interim reports and be informed about study stop/end in agreement with local requirements.

2.6 Declaration of interest

The investigators certify that they have no affiliations with or involvement in any organization or entity with any financial interest (such as honoraria; educational grants; participation in speakers' bureaus; membership, employment, consultancies, stock ownership, or other equity interest; and expert testimony or patent-licensing arrangements), or non-financial interest (such as personal or professional relationships, affiliations, knowledge or beliefs) in the materials analysed in this study.

2.7 Patient Information and Informed Consent

The investigators will explain to each participant the nature of the study, its purpose, the procedures involved, the expected duration, the potential risks and benefits and any discomfort it may entail. Each participant will be informed that the participation in the study is voluntary and that he/she may withdraw from the study at any time and that withdrawal of consent will not affect his/her subsequent medical assistance and treatment.

The participant must be informed that his/her medical records may be examined by authorised individuals other than their treating physician.

All participants for the study will be provided a participant information sheet and a consent form describing the study and providing sufficient information for participant to make an informed decision about their participation in the study. The participant is given enough time (ca. 1 week) to decide whether to participate in the study or not.

The patient information sheet and the consent form will be submitted to the CEC to be reviewed and approved. The formal consent of a participant, using the approved consent form, must be obtained before the participant is submitted to any study procedure.

The participant should read and consider the statement before signing and dating the informed consent form, and should be given a copy of the signed document. The consent form must also be signed and dated by the investigator (or his designee) and it will be retained as part of the study records.

2.8 Participant privacy and confidentiality

The investigator affirms and upholds the principle of the participant's right to privacy and that they shall comply with applicable privacy laws. Especially, anonymity of the participants shall be guaranteed when presenting the data at scientific meetings or publishing them in scientific journals.

Individual subject medical information obtained as a result of this study is considered confidential and disclosure to third parties is prohibited. Subject confidentiality will be further ensured by utilising subject identification code numbers to correspond to treatment data in the computer files.

For data verification purposes, authorised representatives of the Sponsor (-Investigator), a competent authority (e.g. Swissmedic), or an ethics committee may require direct access to parts of the medical records relevant to the study, including participants' medical history.

2.9 Early termination of the study

The Sponsor-Investigator and any other competent authority may terminate the study prematurely according to certain circumstances, for example:

- ethical concerns
- when the safety of the participants is doubtful or at risk, respectively
- alterations in accepted clinical practice that make the continuation of a clinical trial unwise
- early evidence of harm of the experimental intervention

2.10 Protocol amendments

Suggestions regarding study protocol changes are allowed only to direct collaborators in the study (investigators, medical staff), and are internally approved by [name] and [name] before being submitted to the CEC.

Substantial amendments are only implemented after approval of the CEC.

Under emergency circumstances, deviations from the protocol to protect the rights, safety and well-being of human subjects may proceed without prior approval of the sponsor and the CEC. Such deviations shall be documented and reported to the sponsor and the CEC as soon as possible.

All non-substantial amendments are communicated to the CEC within the Annual Safety Report (ASR).

3. BACKGROUND AND RATIONALE

3.1 Background and Rationale

It has been observed that patients subjected to amputations develop so called receptive fields (observations at Rehaklinik Bellikon and Cort X Sensorics), which time of occurrence and localization over time are yet not examined systematically.

A receptive field is defined as skin area ipsilateral to the amputation, which when stimulated by others, causes phantom sensations in the amputated extremity. Phantom Sensations are defined as sensations originating from a body part not connected through the nervous system.

Furthermore, a device has been developed and certified, which can stimulate these receptive fields, and though evoke these sensations, through conventional TENS-Electrodes.

The questions to be answered in the first part of the study are the changes in size and position over time and their timed occurrence after the amputation of these receptive fields as well as the inter-/intratester reliability in their detection.

The testing sequence is explained in sections Study Synopsis and Study Schedule. The monitoring of these fields, which entails no harms to the participants, enables the correct use of the followingly tested stimulation system (Phantom Stimulator, Cort X Sensorics, Spaichingen, Germany) and therefore entails all its benefits.

The question to be answered in the second part of the study is whether in people with lower limb amputation below the knee (prosthesis cannot entail an artificial knee) a "Phantom stimulator" (Cort X Sensorics, Spaichingen, Germany) produces a measurable effect. This effect is measured through changes in gait parameters (gait analysis with OptoGait) and a self-elaborated questionnaire concerning phantom sensations. As above, the testing sequence is described as well in the sections Study Synopsis and Study Schedule.

This treatment constitutes a supplement to the today normally used prosthetic treatment as it upgrades the patient's normal prosthesis by adding a sensory insole, a black box and electrode patches.

Studies investigating the use of this product haven't been done so far, yet important findings have been made regarding the reduction of phantom limb pain thanks to enhanced sensory input from the lost extremity.

- Katz J. (1991); Auricular Transcutaneous Electrical Nerve Stimulation (TENS) reduces Phantom Limb Pain; Journal of Pain and Symptom Management 6 (73-83)

3.2 Investigational Product and Indication

Product name: Phantom Stimulator

Model: PST 3010 2 channel stimulator with separate outputs for heel and ball Auto Power On and Power OFF function (sleep / wake-up function) 15 integrated setting-wide (frequency / amplitude / intensity) Power supply: 7.4 VDC (Integrated LIPO rechargeable) Power consumption: = 40 mA (treatment); = 30 μ A (power down) Electr. supply capacity: 760 mAh (calculated range approx. 10 hrs.) Dimensions: 76 x 44 x 22 mm (H x B x T) Weight: 60 g without battery Output current: 0.5 - 6 mA (on 1 kOhm load) Output voltage: max. 36 volts (1 kOhm load) Pulse shape: positive rectangle with a negative share (bi-phase / mono-phase) Frequency range: 5 - 150 Hz Pulse width: 75 μ s - 100 ms

Working conditions:

Temperature: 5 to 40°C Relative Humidity: 30% to 90% Storage Temperature: -20 to 60°C Relative Humidity: 10% to 90%

Available Accessories/Replacement Parts

Long life electrode pads - 25 mm round (set of 4) Long life electrode pads - 45 mm square (set of 4) Electrode extension cord - 0.5 meter length Electrode extension cord - 0.75 meter length Electrode extension cord - 1.0 meter length

Further relevant information is provided separately in the attached user manual.

The device needs a training (1000 Steps) and installation prior to use. Indications for the use of the device are the bearing of a lower limb prosthesis without artificial knee.

3.3 Preclinical Evidence

Not applicable.

3.4 Clinical Evidence to Date

To date there is no clinical research data available on the investigational product.

3.5 Rationale for the intended purpose in study (pre-market MD)

The device is used for a duration 1 day during the intervention. During this period, the device complementing the prosthesis is worn for at least 2x1000 steps.

These times have been selected to allow the patients enough time to adapt to the system.

The application of the system is as follows:

• For the intervention, the electrodes have to be placed on the correspondent receptive fields (heel and ball) so to allow the wanted sensory feedback.

The selected device as well as the defined timespan with the functioning device allows us to detect the positive effects on gait parameters and phantom sensations, thus providing important information for improvements of the quality of life of the target group.

3.6 Explanation for choice of comparator (or placebo)

As the direct effects of the system have to be measured, the natural choice for a placebo group (in our cross over design) is to use the exact same setup. Only difference being that the system remains in an unfunctional state during the whole testing period.

In this manner, we exclude the weight or the simple sight of the attached system to have any influence on our measured results.

3.7 Risks / Benefits

The benefit/risk relationship for our patients is very high, as there are potentially no risks coming from the device or the performed tests. This as the device is only used in its described purposes in the CE certification, and as all the performed tests are well established and safe to perform. The benefit of this study consists in a better understanding of the receptive fields and better application of such stimulation systems improving the quality of life.

Relevant information to this section is given in the attached user manual.

3.8 Justification of choice of study population

For the implementation of the study on the description of the receptive fields we selected a relatively wide range of people with lower limb amputation, to expand the number of participants to a maximum. We excluded people only with amputations of the upper limbs as to confine the results of this study on lower limb amputees which can also benefit from the tested stimulating system.

For the implementation of the study on the stimulating system we selected a population with lower limb amputations to apply the system on. We excluded people with an amputation site proximal the knee because of the unknown influence the several types of prosthetic knees could have on the study outcome.

We guarantee that signs and symptoms showing that a participant is unwilling to participate in the study will result in the exclusion of the participant from the study. Further we guarantee that a physician not participating in the study, safeguards the participants interests and insures proper medical care.

Finally, we do not recruit participants that are incapable of judgement, minors or under tutelage.

4. STUDY OBJECTIVES

4.1 Overall Objective

The question to be answered through this study is how the receptive fields of lower limb amputees behave in size and position over a timespan ranging from 1 day to 1 month. Further, the intra-/intertester reliability of the proposed detection method for the receptive fields should be assessed.

4.2 Primary Objective

The study seeks to evaluate the behaviour of the receptive fields of lower limb amputees in size and position over a timespan ranging from 1 day to 1 month.

4.3 Secondary Objectives

Secondary objectives are:

- Intra-/intertester reliability of the proposed detection method
- Influence of the Phantom Stimulator (Cort X Sensorics, Spaichingen, Germany) on selected gait parameters and phantom sensations

4.4 Safety Objectives

As the safety of the detection method is out of discussion no safety objectives are set.

As the safety of the stimulation system has already been proven for the certification with the CE label, in this study we do not analyse safety aspects related with the use of the "Phantom Stimulator" (Cort X Sensorics, Spaichingen, Germany).

5. STUDY OUTCOMES

5.1 Primary Outcome

The primary measured outcome is the evolution/difference in size and position/movement of the detected receptive fields. This is done in the unit of cm^2 .

This is done comparing size and position of the same receptive fields between day 1, 2, 7, 14, 21, 28 and 31 of the study.

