	(Streuung) between	similar population sub	ogroups (chronic pain		
	patients) is of 0.27%.				
	Therefore, the effect size is d = 1.11 with μ_i = 0.3 and SD = 0.27.				
	We set the significant	ce level at 5% and the p	power at 0.8.		
	Using the paired t-tes	t these values originate	e the following N's:		
	μ _i	d	Ν		
	0.25	0.93	40		
	0.3 1.11 28				
	0.35 1.23 24				
	As we assume a dropout rate of 10% we aim at 31 Participants for				
	the duration of this st	udy.			
Study Duration:	For each subject, the	study lasts about 5 to 6	6 weeks.		
Study Schedule:	First subject: 24.10.2	017			
	Last subject: 08.05.2018				
Investigator(s):	[name],				
	Sportmedizin und Re	habilitation			
	[name]				
Study Centre(s):	Rehaklinik Bellikon				
	[name]				

Statistical	ical Statistical Analysis:				
Considerations:	The statistical analy and "Excel".	ysis is performed wi	th the program "R"		
	For the primary outcome, the pictures are evaluated for size and position with the computer program "Photoshop". We define a change in size if a difference of more than 10% is detected in comparing a receptive field of two measurements. We define a change in position if the summed area of the two overlapping receptive fields exceeds the area of the bigger of the two single receptive fields by more than 20%. So, if the two receptive fields overlap completely (even if different in size) we do not count it as a change in position (only change in size).				
	For the secondary parameters of 10 rur compared between th	outcomes; a mean fo ns of gait analysis is c ne two randomized proto	or every one of the reated. These data is ocols (A and B).		
	All the results are tre 0.05 is achieved.	ated as significant if th	e significance level of		
	Power Analysis/Sam	nple size:			
	As this study is a first in this field (Pilot), regarding literature is not present and different assumptions (professional guesses) must be made.				

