5.2 Secondary Outcomes

The secondary outcomes are measured as follows:

- The intratester reliability is evaluated by comparing size and position of the same receptive fields within 1 week detected by two different investigators.
- The intertester reliability is evaluated by comparing size and position of the same receptive field within 1 week detected by the same investigator.
- Influence of the stimulating system on phantom sensations and gait parameters is measured through the evaluation of a questionnaire concerning the phantom sensations, and through the analysis of a gait analysis (step width, step length, cadence, floor contact time and walking speed).

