9.2 Assessments of outcomes

9.2.1 Assessment of primary outcome

The primary measured outcome is the evolution/difference in size and position/movement of the detected receptive fields. This is done in the unit of cm^2 .

To record the data needed to compare the receptive fields is collected as follows:

- Day 1: detection of the receptive fields by one single tester at a self-selected time of day.
- Day 2: detection of the receptive fields at the same time of day as on day 1 by the same tester as on day 1.
- Day 7: detection of the receptive fields at the same time of day as on day 1 by the same tester as on day 1.
- Day 14: detection of the receptive fields at the same time of day as on day 1 by another tester as on day 1.
- Day 21: detection of the receptive fields at the same time of day as on day 1 by the same tester as on day 1.
- Day 28: detection of the receptive fields at the same time of day as on day 1 by the same tester as on day 14.
- Day 31: detection of the receptive fields at the same time of day as on day 1 by the same tester as on day 1.

The expression "same time of day" stands for:

-at maximum 1-hour difference in timing between the measurements.

-similar sleeping and dietary pattern 12 hours prior the measurement (assessed through a questionnaire).

The detection of the receptive fields is planned as follows:

- 1. performed by two specifically trained persons
- 2. performed through tactile stimulation of the skin surface with a brush (mild toothbrush or similar).
- 3. the receptive fields are determined through the dialogue with the participant. Here he can signal the presence of a receptive field with the word "Yes". Important in this setup is that the participant does not look at the inspected site or the tester.
- 4. the receptive fields are drawn on to the skin with a commercial eyeliner pencil.
- 5. the drawn receptive fields are photographed from different locations under standardized conditions (distance and angle).
- 6. this photo is imported in the program Photoshop (Adobe Photoshop Version 2017.1.1) where the respective area and position can be determined.

As a change in size is defined as a difference of more than 10% when comparing the same receptive field of two separate times.

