We define as a change in position if the area of the two overlapping areas exceeds the area of the bigger of the two single areas by more than 20%. So, if the two areas overlap completely (even if different in size) we do not count it as a change in position.

As every meeting last approximatively one hour, we estimate a total duration of about 7 hours for this phase of the study.

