11. STATISTICAL METHODS

11.1 Hypothesis

Null Hypothesis:

- 1) Receptive fields do not change in position and size over the various measured time intervals
- 2) The intra-/intertester reliability concerning the proposed detection system is good and therefore no difference in detection are seen
- 3) The stimulating device has no effect on the participants performing a gait analysis (selected parameters) and answering a questionnaire regarding phantom sensations

Alternative Hypothesis:

- 1) The position and size of the detected receptive fields changes significantly over the various measured time intervals
- 2) The intra-/intertester reliability concerning the proposed detection system is imperfect and therefore difference in detection can be seen
- The stimulating device has a significant effect on the participants performing a gait analysis (selected parameters) and answering a questionnaire regarding phantom sensations

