11.2 Determination of Sample Size

As this study is a first in this field (Pilot), regarding literature is not present and different assumptions (professional guesses) must be made.

We define a change in size of the receptive field if over the 31 days the size change is of more than 10%.

We anticipate a change in size and position of 30% of the measured receptive fields between day 1 and 31 to be clinically significant for the purposes of our and further studies. In this case significant means that the attached electrodes at day 1 would not be touching the receptive field anymore at day 31.

From previous studies concerning the two-point discrimination (Catley M. J. (2014)) we know that the standard deviation (Streuung) between similar population subgroups (chronic pain patients) is of 0.27%.

Therefore, the effect size is d = 1.11 with $\mu_i = 0.3$ and SD = 0.27.

We set the significance level at 5% and the power at 0.8.

_	-	_
μi	d	Ν
0.25	0.93	40
0.3	1.11	28
0.35	1.23	24

Using the paired t-test these values originate the following N's:

As we assume a dropout rate of 10% we aim at 31 Participants for the duration of this study.

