11.4.2 Primary Analysis

At the end of the 31-day period making up the first part of the study, the datasets concerning the receptive fields are evaluated by the principal investigators ([name], [name]).

Here, next to the numerical tables exhibiting the monitored changes in size and position of the receptive fields, a graph will be made explaining the occurrence of these fields in relation to the time since the amputation occurred.

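### Intra- and intertester labels are swapped, days 14 and 28 mix tester with time, and the 10% and 20% change rules are never read against the day 1–2 retest data

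*Combined protocol and SAP*

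**What the plan says.** **Primary outcome.** Section 5.1 assesses it by "comparing size and position of the same receptive fields between day 1, 2, 7, 14, 21, 28 and 31".

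**Change rules.** Section 9.2.1 sets the size rule: "As a change in size is defined as a difference of more than 10% when comparing the same receptive field of two separate times". Section 11.2 applies it to the whole period: "We define a change in size of the receptive field if over the 31 days the size change is of more than 10" per cent. For position, a change is counted in section 9.2.1 when the combined area "exceeds the area of the bigger of the two single areas by more than 20" per cent. The Synopsis (Statistical Considerations) words this as the "summed area of the two overlapping receptive fields exceeds the area of the bigger of the two single receptive fields by more than 20" per cent.

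**Hypothesis and analysis.** Section 6.1 calls part one purely descriptive, but the alternative hypothesis in section 11.1 reads "The position and size of the detected receptive fields changes significantly over the various measured time intervals". Section 11.4.2 plans "numerical tables exhibiting the monitored changes in size and position of the receptive fields" and a graph of field occurrence against time since amputation.

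**Reliability.** Section 5.2 states: "The intratester reliability is evaluated by comparing size and position of the same receptive fields within 1 week detected by two different investigators". It then defines intertester reliability by a single investigator. Sections 11.4.1 and 11.4.3 assign days 1 and 2 to intertester and days 28 and 31 to intratester reliability. Section 9.2.2 describes both types as a comparison between two testers.

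**Testers.** Sections 9.1 and 9.2.1 give tester A on days 1, 2, 7, 21 and 31, and tester B on days 14 and 28. The data sheet in section 11.4.1 lists six overlaps with day 1: days 2, 7, 14, 21, 28 and 31.

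**The concern.** The primary question is whether receptive fields change within a month. A field is found by brushing the skin until the participant says yes, and its outline is then drawn by hand. Two drawings of an unchanged field will therefore differ to some degree. If a fixed percentage is called change without knowing how often two drawings a day apart exceed it, a share of the reported changes may be redrawing error. On days 14 and 28, any habitual difference between the testers adds to this and appears as an effect of time.

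The label swap affects a stated secondary objective (section 4.3). Followed as written, both reliability results would be reported under the wrong name.

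**Working it through.** **1. Labels against the tester schedule**

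- Days 1 and 2: testers A and A. This is a same-tester pair, so intratester. Sections 11.4.1 and 11.4.3 call it intertester.
- Days 28 and 31: testers B and A. This is a two-tester pair, so intertester. The same sections call it intratester. It also contains three days of elapsed time.
- The outcome definition, data sheet and analysis text all agree with each other, so this is a systematic swap and not one slip.

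**2. Tester against time**

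Of the six overlaps with day 1, days 2, 7, 21 and 31 are A v A, and days 14 and 28 are A v B. Two of six mix tester with time. Day 1 v 31, the contrast used in section 11.2, is A v A. The documents do not say whether the two people exchange roles across participants. Exchange would balance group mean size but not the change flagged in a single field.

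**3. Change rules against retest error**

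The plan has no retest figure to reproduce. Its only SD (0.27, section 11.2) concerns two-point discrimination in chronic pain subgroups. Everything below is an assumption, with no true change.

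*Size rule.* With single-session coefficient of variation CV, P(flag) = 2 × [1 − Φ(0.10 / (CV × √2))].

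- CV 3%: 0.10/0.0424 = 2.36, giving about 2%.
- CV 5%: 0.10/0.0707 = 1.41, giving about 16%.
- CV 10%: 0.10/0.1414 = 0.71, giving about 48%.
- The share stays at or below 5% only if CV is about 3.6% or less.

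*Tester effect at CV 5%, log scale.* The SD of the log ratio is √2 × √ln(1 + 0.05²) = 0.0707.

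- Tester B draws 5% larger: 1 − [Φ((ln 1.1 − ln 1.05)/0.0707) − Φ((ln 0.9 − ln 1.05)/0.0707)] = 1 − [Φ(0.66) − Φ(−2.18)], about 27%.
- Tester B draws 10% larger: 1 − [Φ(0) − Φ(−2.84)], about 50%.
- These apply to days 14 and 28, against 16% on tester-A days.

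*Position rule.* I read it as the union of the two fields against the larger one. The sentence that exempts complete overlap requires this. For two equal circles of radius r, the 20% line is crossed when overlap falls below 80%, at a shift of 0.3155r: 4.7, 7.9 and 15.8 mm for fields 3, 5 and 10 cm across. With per-axis session error s, P(flag) = exp(−shift²/(4s²)). At s = 3 mm this gives 54%, 18% and 0.1%.

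Equal circles overstate the risk, because a smaller field that shifts inside a larger one adds no area. A simulation of two circles with CV 5% in area as well gives, at 3 mm, about 43%, 10% and under 0.1%. Other cases fall similarly: 25% to 16% (3 cm, 2 mm) and 38% to 27% (5 cm, 4 mm).

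*Both rules at once.* In the same simulation, error meets the size and the position rule together in about 0–8% of fields (CV 5%, 3–10 cm, 2–4 mm).

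**The case against.** Part one is a descriptive pilot. The outcome is in cm², section 11.4.2 promises numerical tables, and no passage says the share of flagged fields is the reported result. Section 9.2.1 requires trained testers, standardised photographs, a one-hour time window and similar sleep and diet. Section 12.2.4 averages three photo measurements by two investigators. Section 6.2.3 lists the reliability analysis as a guard against bias, and the Synopsis counts it among the primary outcomes. A careful reader can recover the right labels from the printed days and testers.

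Much of this stands. The raw material for a benchmark is planned, and the standardisation limits error. But it does not measure redrawing error, and averaging the photo reading leaves repeat detection on the skin untouched. No section says how the day 1–2 result bears on a flagged change, while section 11.1 states a hypothesis of change.

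Three stronger readings are tempting and not supported:

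- *Noise alone could produce the 30% in section 11.2.* A CV of 6.8% does flag 30% by the size rule, but that CV has no source in the documents. Section 11.2 and the Synopsis sample-size rationale say size *and* position; only the power paragraph under Statistical Considerations says *or*. Error meets both rules far less often. Section 11.2 also explains significance as day-1 electrodes no longer touching the field, which is stricter than a 10% area difference.
- *The 10% rule contradicts itself.* Section 9.2.1 gives the general rule for any two measurements, and section 11.2 applies it to days 1 and 31.
- *The tester change spoils the main contrast.* Day 1 v 31 keeps one tester.

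**Conclusion.** The concern holds on three counts. The label swap and the tester schedule are read directly from the text and need no assumption. The missing link between the change rules and retest error is also plain, but its size is unknown: from about 2% to 48% of unchanged fields for size over CVs of 3–10%, and from under 0.1% to about 43% for position at 3 mm error and CV 5%, depending on field diameter. These figures assume circular fields, log-normal or normal error, and the same error at both visits. The problem may be negligible or large, and the day 1–2 data will help show which. It does not make the primary data unusable. It should be settled before the data are read, because afterwards the choice of what counts as change would depend on the result.

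**What to change.** 1. **Labels.** In sections 5.2, 9.2.2, 11.4.1 and 11.4.3, call days 1–2 intratester, and days 28–31 intertester plus three days of elapsed time.
2. **Tester.** In sections 5.1, 11.4.1 and 11.4.2, base the main time course on tester-A days (day 1 v 2, 7, 21 and 31). Show days 14 and 28 marked as tester B and read them as time plus tester.
3. **Benchmark.** In section 11.4.2, report the share of fields flagged on day 1 v 2 beside day 1 v 31, for size and for position. Do not read the day 1 v 31 share as change unless it exceeds the day 1 v 2 share. State three limits:
   - Day 1–2 includes any true one-day change.
   - Simple subtraction understates the true share. If 30% truly change and all are flagged, with 16% error the day 31 share is 0.30 + 0.70 × 0.16 = 0.412, and 0.412 − 0.16 = 0.252. Dividing by 1 − 0.16 returns 0.30.
   - The benchmark assumes similar retest error at 1 and 30 days. Recall of the previous day's field would make it too small.
4. **Criterion.** Reconcile size *and* position (section 11.2 and the Synopsis sample-size rationale) with size *or* position (Synopsis, Statistical Considerations).

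Optional: a sensitivity cut-off for size based on the SD of day 1–2 differences, and a size comparison of day 14 with the mean of days 7 and 21, where linear drift cancels.

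**Cost.** No new visits or measurements, only wording. The main time course has two fewer points, and the claimed share of changed fields will probably be smaller.
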